We propose a randomized trial of a multifaceted intervention designed to optimize a patient-centered approach for improving adherence to prescription opioids, “Improving the Safety of Opioid Prescriptions (ISOT).” Primary care clinicians and PACT (Patient Aligned Care Team) nurses will be randomized to ISOT or the control condition; patients will be nested by clinician status. Clinicians and PACT nurses in both groups will participate in an interactive workshop on reducing prescription opioid abuse and enhancing safety. In addition, clinicians assigned to ISOT will work with a nurse care manager (NCM) who will maintain a registry of enrolled patients, track UDT administrations and results, examine state Prescription Drug Monitoring Program data, monitor medical records, and collaborate with an internist and substance abuse specialist to provide decision support when patients demonstrate evidence of prescription opioid misuse or abuse. The NCM will also meet with intervention patients to discuss strategies for reducing opioid adverse effects and preventing diversion, and to provide rationale for prescription opioid adherence monitoring. Thus, our intervention targets system, clinician, and patient levels. A research goal is to enhance patient-centered pain care and improve the quality of the communication and relationship between the patient and the primary care team pertaining to this challenging topic. The main objectives of this study are to evaluate the efficacy and acceptability of a multifaceted intervention (ISOT) to enhance opioid safety in patients with chronic pain.

SPECIFIC AIMS

Aim 1: Evaluate to what extent a multifaceted intervention (ISOT) enhances prescription opioid safety.

Hypothesis 1: At 12 months, ISOT patients will have lower rates of prescription opioid abuse, as assessed via multiple methods (self-report, clinical interview, urine drug testing), compared to patients of clinicians randomized to the control condition.

Hypothesis 2: At 12 months, ISOT patients will experience fewer adverse events (defined in this proposal to include emergency room visits, overdoses, falls, motor vehicle accidents).

Aim 2: Assess to what extent assignment to ISOT impacts pain treatment-related processes of care.

Hypothesis 1: ISOT patients will have more modifications to clinical care documented in the medical record, including more frequent UDTs and queries to state prescription drug

monitoring programs.

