Hypothesis 2: ISOT patients will report greater trust and satisfaction with their PCP related to opioid prescribing and treatment of chronic pain, relative to patients in the control condition.

Aim 3: Explore to what extent ISOT is associated with changes in pain intensity, function, quality of life, and depressive symptoms.

Hypothesis: ISOT patients, relative to patients in the control condition, will not experience worse significant adverse outcomes in pain intensity, function, quality of life, or depressive symptoms.

If ISOT is effective, we will additionally examine intervention impacts on VA healthcare utilization and costs.

The **overall significance** of this project is to test the efficacy, satisfaction, and cost-effectiveness of a multifaceted patient-centered intervention designed to enhance opioid safety. Results will inform the utility of team-based care and risk mitigation strategies for chronic opioid therapy. If results are significant, clinicians will have a pragmatic evidence-based treatment that improves adherence to prescription opioids, reduces adverse events, does not result in impairments, and enhances the clinician-patient relationship.

BACKGROUND

The use of prescription opioid medications to treat chronic pain continues to increase.¹⁵ Data on opioid efficacy for chronic pain is limited.¹⁶ Studies indicate one-half of patients prescribed opioids will receive up to 30% improvement in short-term pain intensity.^{17,18} Less data are available on the long-term benefit of opioids.^{19,20}

Recent statistics are emerging about harms associated with the use of prescription opioids – this includes issues of misuse, abuse, diversion, and opioid-related adverse events. Prescription opioid misuse includes taking more medication than prescribed, requesting early refills, or using opioids for a non-prescribed purpose; this may occur in up to two-thirds of patients prescribed chronic opioid therapy (COT).^{8,9} More severe prescription opioid abuse, which includes concurrent illicit substance use and alcohol abuse, occurs in 10-35% of patients prescribed COT.^{10,21} Concurrent use of prescription opioids and alcohol or illicit substances increases likelihood of adverse effects, including overdose, and inhibits effective pain treatment.²³

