During the screening telephone call, the study research assistant will provide a brief overview of the study purpose (including clear statements that participation involves research and participation does not provide clinical treatment), review inclusion/exclusion criteria, describe what participation in the study would entail, and schedule participants for a study appointment session. If the patient is interested in participating and eligible, the patient will be scheduled for a baseline assessment (participants will also receive reminder phone calls and/or letters prior to their scheduled appointment). To enhance the likelihood of participants attending the study evaluation session, we will offer a \$50 payment in compensation for time and/or travel to attend the research visit. The baseline assessment and all follow-up evaluations will be conducted either in person or via telephone.

During the telephone screening visit, if the participant is ineligible, but is interested in receiving additional clinical services, s/he will be referred to the study PI to contact for information about relevant clinical resources.

During the assessment sessions, the research assistant will provide another overview of study participation, administer informed consent and HIPAA authorization, and instruct the participant to complete study measures.

Follow-up: In addition to the baseline assessment, all participants will complete follow-up assessments every 6 months. During these research visits, participants will complete all study measures (described below). Research visits must be completed within 1 month of the scheduled follow-ups (i.e., the 6-month follow-up must be completed between 5-7 months from baseline and the 12 month follow-up must be completed between 11-13 months from baseline).

Randomization: We will randomize by PCP; patients will be assigned to intervention or control based on randomization of their PCP and PACT nurse. At the VAPORHCS, each PACT nurse is assigned to a single PCP and each PCP has one PACT nurse. Thus, contamination effects by PACT nurses working with a PCP assigned to the control condition will not be a concern.

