We will randomize dyads of PCPs and PACT nurses to receive ISOT versus control. We will initially recruit PCPs to participate. Of the PCPs who choose to enroll, we will then attempt to recruit the PACT nurse who is assigned with that PCP (if the PACT nurse chooses not to participate, the consenting PCP will remain eligible). We will randomly assign consenting PCPs and their PACT nurse (if they choose to participate) to receive ISOT versus control after stratifying by PCP type of training (physician versus nurse practitioner/physician assistant) and proportion of patients in PCP's panel receiving opioid prescriptions (high vs low, based on median eligible clinician population). Using a permuted block randomization and maximizing the number of PCPs (clusters) should prevent major uneven distribution of caseload size and unmeasured confounders across the arms and increase precision.⁷² The statistician will perform the randomization prior to patient recruitment. Research assistants will be blind to intervention status of patients and clinicians.

ISOT Team and Training: ISOT is a multifaceted intervention. The individual components of ISOT have been adapted from recommendations made as part of clinical practice guidelines^{11,16}, our preliminary studies, and prior experience in conducting multifaceted intervention studies in primary care.^{48,51} The unique aspect of this intervention is its integration of different treatment recommendations into a single package. This method of treatment development and adaptation is similar to other effective multifaceted interventions.⁷³

A research nurse care manager (NCM) will be hired to participate in this study. The NCM will be employed full-time. S/he will have clinical training as a registered nurse (R.N.) and have a clinical background in chronic disease management and outpatient treatment. The individual will receive extensive training in chronic pain management, prescription opioid safety, and research procedures.

ISOT Intervention Components

Clinician Education and Activation:

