observations on different patients of the same PCP and for repeat observations on the same patient. Transformations of the outcome will be applied to meet distributional assumptions. In linear mixed models, we will include baseline measures of patient age, sex, depressive symptoms, history of SUD, and pain severity as covariates. We will also adjust for baseline COMM score and the stratification variables: PCP training type (MD/DO vs NP or PA) and proportion of clinician panel prescribed opioids (high vs low). In addition to testing formal hypotheses, we will report 95% confidence intervals for the differences in mean outcomes between groups at 6 and 12 months. For comparing the percentages classified as abusing opioids at any time during follow-up (combining information from 6 and 12 months) based on SCID and UDT, we will use generalized-linear mixed models (or GEE as needed) to incorporate correlation between patients of the same PCP. We will adjust for baseline measures of the outcome along with the covariates listed above. We will report group comparisons on all three primary outcomes (COMM, SCID, and UDT). Assuming 15% of the sample has current SUD (consistent with other research), we will not conduct interaction analyses, but will present descriptive information for each outcome (COMM, SCID, UDT) on treatment outcomes by SUD status.

Data on opioid-related adverse events will be obtained from the medical record and participant self-report. We will collect data on opioid overdoses, falls, motor vehicle accidents, and ER visits related to pain. Descriptive information on opioid-related events will be provided for each group (numbers and percentages of participants with each event). Because the number of adverse events is expected to be small, we will use Fisher's Exact test to compare adverse event percentages between groups. We will compare both percentages for each individual type of event as well as percentages of individuals experiencing any adverse event between groups.

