Aim 2: Assess to what extent assignment to ISOT impacts pain treatment-related processes of care. The power for comparing the percentage of patients receiving at least one UDT (Table 2) during the follow-up period assumes that 40% of patients in the control group will receive a follow-up UDT.²¹ This is based on prior research in which 26% of patients had a UDT and our expectation that the percentage will be higher in the control group after clinicians participate in the workshop. We hypothesize that clinicians randomized to ISOT will have much higher rates of administering UDTs. Regarding checks to state PDMPs, currently 3-5% of VAPORHCS patients receive a query. The ISOT protocol prompts the clinician to conduct PDMP queries and we expect dramatic differences in percentages between the two intervention groups. We have 80% power to detect differences of 17-21% on binary outcomes. Here we expect differences to be much greater.

Table 2. Urine drug test percentage in the intervention group that can be detected (80% power, $\alpha=0.05$) *compared to a usual care percentage of 40%*.

Intra-class correlation	Urine drug test % that can be detected in the intervention group, n=4 patients per clinician, 28 clinicians per intervention	Urine drug test % that can be detected in the intervention group, n=4 patients per clinician, 32 clinicians per intervention	Urine drug test % that can be detected in the intervention group, n=5 patients per clinician, 28 clinicians per intervention	Urine drug test % test that can be detected in the intervention group, n=5 patients per clinician, 32 clinicians per intervention
0	59%	57%	57%	56%
0.02	59%	58%	57%	56%
0.04	60%	58%	58%	57%
0.10	61%	60%	60%	58%

Aim 2: Assess to what extent assignment to ISOT impacts the quality of the clinician-patient relationship. Using estimated standard deviations of 14.2 for the Trust in Physician Scale⁸⁴ and

28.9 for the Participatory Decision Making Style,⁸⁶ we have 80% power at level 0.05 to detect mean differences between groups at 12 months of 4.7 to 5.6 and 9.6 to 11.3, respectively, using 28 to 32 clinicians per intervention group, 4 to 5 patients per clinician, and assuming an intraclass correlation of 0.02. If we focus on change from baseline, the power for comparisons at each follow-up time-point would be greater, provided the correlations between baseline and follow-up are greater than 0.5.

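### Adverse events are tested with a patient-level Fisher's exact test although PCPs are randomised, so the 5% level is not protected for commoner endpoints if the ICC nears 0.10

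*Combined protocol and SAP*

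**What the plan says.** Under *Randomization*, the PCP is the unit: "patients will be assigned to intervention or control based on randomization of their PCP and PACT nurse". Allocation is stratified by type of PCP training and by the share of the PCP's panel receiving opioids.

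Under *Analyses for Aim 1*, the COMM model has a random PCP effect, and the SCID and UDT percentages are compared with "generalized-linear mixed models (or GEE as needed) to incorporate correlation between patients of the same PCP". The next paragraph turns to adverse events: overdoses, falls, motor vehicle accidents and pain-related ER visits. It plans Fisher's "Exact test to compare adverse event percentages between groups", because few events are anticipated. The test is to be applied to each event type and to "percentages of individuals experiencing any adverse event between groups". No section deals with clustering for adverse events. The *Data Analysis* introduction mentions clustering only for the power calculations, and there is none for adverse events.

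The endpoint carries a formal hypothesis in the *Specific Aims*: "At 12 months, ISOT patients will experience fewer adverse events". The conclusion foreseen there is a treatment that "improves adherence to prescription opioids, reduces adverse events, does not result in impairments".

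**The concern.** Fisher's test treats each patient as independently allocated. Here patients of one PCP are allocated together, and their outcomes may be correlated. A patient-level test then understates the variance of the between-arm difference and can reject too often. Sparse data are a good reason for an exact method, but not for taking the patient as the unit.

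At stake is the error rate of the only between-group test planned for Aim 1, Hypothesis 2. The comparison of any adverse event is the most exposed: it pools four event types, so it is at least as common as the commonest of them. Adverse events are not among the three outcomes the plan calls primary.

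**Working it through.** **Inputs from the plan.** The target is 32 PCPs per arm with an average of 5 patients (160 per arm). The loss scenario is 28 PCPs with 4 patients (112 per arm). ICCs of 0, 0.02, 0.04 and 0.10 come from Tables 1 and 2, which concern COMM and UDT. The level is 0.05, taken as two-sided.

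**Assumed, not in the documents.** Event rates of 2% to 40%; beta-binomial variation between PCPs; the uneven caseload patterns; the sizes of the randomisation strata.

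**Step 1: the plan's own clustered calculation.** The plan gives no error or power figure for adverse events, so Table 2 is the nearest benchmark. The effective sample per arm is mk/DEFF, where DEFF = 1 + (m − 1) × ICC for m patients in each of k PCPs. For 28 × 4 at ICC 0.10, DEFF = 1 + 3 × 0.10 = 1.30 and 112/1.30 = 86.2. A two-sided 5% test of two proportions (pooled variance, 40% control rate, 80% power) then detects 61.2%; the table has 61%. All 16 cells of Table 2 agree after rounding, so the plan's power work does allow for clustering.

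**Step 2: what ignoring clustering does to a simple z test.** Its size is 2 × [1 − Φ(1.96/√DEFF)]. For m = 5:

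- ICC 0.02: DEFF 1.08, size 5.9%
- ICC 0.04: DEFF 1.16, size 6.9%
- ICC 0.10: DEFF 1.40, size 9.8%

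Fisher's test is conservative and absorbs part of this, so its size has to be computed exactly.

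**Step 3: exact size of Fisher's test.** Each PCP's event count is beta-binomial with the given rate and ICC. The PCP counts are convolved to arm totals, and the probability of p < 0.05 is summed under equal rates in the two arms. For 32 × 5:

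| Event rate | ICC 0 | 0.02 | 0.04 | 0.10 |
|---|---|---|---|---|
| 2% | 1.3% | 1.7% | 2.0% | 3.3% |
| 5% | 2.5% | 3.1% | 3.8% | 5.8% |
| 10% | 3.3% | 4.0% | 4.7% | 7.1% |
| 20% | 3.6% | 4.4% | 5.2% | 7.7% |
| 30% | 3.8% | 4.6% | 5.4% | 8.0% |
| 40% | 3.7% | 4.5% | 5.3% | 7.8% |

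The size passes 5% from an ICC of about 0.17 (2% rate), 0.08 (5%), 0.05 (10%), 0.04 (20%) or 0.03 (30%).

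For 28 × 4 the maxima over these rates are 3.6%, 4.2%, 4.8% and 6.6% at ICC 0, 0.02, 0.04 and 0.10.

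**Step 4: uneven caseloads.** The plan fixes only an average of 5 patients per PCP. With caseloads of 1, 2, 3, 4, 5, 6, 8 and 11, repeated four times per arm (mean 5, CV 0.62), the maxima are 5.0% (ICC 0.02), 6.2% (0.04) and 10.0% (0.10). With a more skewed pattern (CV 0.75) and a 30% rate they are 5.2%, 6.6% and 11.0%.

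**Step 5: tests at the PCP level.** A test permuting PCPs within four strata was simulated with 1,999 re-allocations per trial and 4,000 to 8,000 trials per setting. The Monte Carlo standard error of size is about 0.2 to 0.35 points. Its size was:

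- 1.2% to 4.1% for 32 × 5, ICC 0 to 0.10
- 0.5% to 4.0% for 28 × 4, ICC 0.02 to 0.10
- 4.4% to 5.2% for uneven caseloads (CV 0.67), rates of 5% to 30%, ICC 0.02 to 0.10

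A different method, a t-test on PCP-level proportions, gave 4.8% to 4.9% for 32 × 5 at ICC 0.10 with rates of 5% to 40%.

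**The case against.** The plan expects few events, and there Fisher's test does little harm. At a 2% rate its size stays below 5% at every ICC in Tables 1 and 2, and is 4.4% even with caseload CV 0.62 and ICC 0.10. With equal caseloads, a size above 7% needs both an event rate of about 10% or more and an ICC near 0.10.

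That ICC is borrowed. Ordering a UDT is clinician behaviour, whereas falls and accidents are patient events. In the beta-binomial model, a 10% mean rate with ICC 0.10 implies true PCP rates from about 1% to 23% (10th to 90th percentile), against about 5% to 16% at ICC 0.02. The single value the plan uses for the relationship scales is lower: "assuming an intraclass correlation of 0.02". The size calculation also ignores stratification. Any part of the ICC explained by the strata is balanced between arms, so it would not add to the inflation. Finally, a PCP-level test loses some power where Fisher's test already holds its level.

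All of this stands, and it limits the weight of the point. It does not make the patient the right unit. Under the planned test, the 5% level holds only if an unstated event rate or an unstated ICC happens to be low. A test based on the actual randomisation does not depend on either.

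**Conclusion.** The concern holds. The wrong unit of analysis follows directly from the text and is inconsistent with the treatment of SCID and UDT in the same section. The inflation is modest and conditional. With equal caseloads at the target size and rates of 10% or more, the true size is about 7% to 8% at ICC 0.10, around 5% at 0.04 and below 5% at 0.02. Uneven caseloads can bring it to about 10% at ICC 0.10. Rare single events are little affected. These sizes rest on assumed event rates, ICCs borrowed from other outcomes, beta-binomial clustering and, where stated, assumed caseload patterns. The plan should be changed, but the primary outcomes are not touched.

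**What to change.** Replace Fisher's test in every adverse-event comparison with one pre-specified two-sided test. The statistic is the difference in the percentage of patients with the event. Its reference is the exact or Monte Carlo distribution from re-allocating PCPs between arms within the randomisation strata. This serves sparse and common events alike and needs no count threshold. Keep the planned counts and percentages.

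Optionally, for any adverse event only, add the PCP-clustered GLMM or GEE already planned for SCID and UDT, to give an effect estimate with a 95% confidence interval. State that the permutation p-value governs the hypothesis test. The model option was not simulated.

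The cost is one SAP sentence, a few lines of code and some power. For an assumed 20% versus 8% at 32 × 5, simulated power of the permutation test against Fisher's test is:

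- 82% versus 85% at ICC 0.02
- 78% versus 83% at ICC 0.04
- 71% versus 81% at ICC 0.10, where part of Fisher's apparent advantage comes from its inflated size

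The standard error of these power figures is at most 0.8 points. The permutation test is also conservative when events are very sparse (size 0.5% to 1.4% at a 2% rate).

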- a. The NCM will maintain a registry of all enrolled patients and track UDT administrations. For patients that have not been administered a UDT in 12 months or more, the NCM may assist the PCP by placing an order for UDT in the medical record.
- b. The NCM may write the UDT order for the PCP to sign, if requested. The NCM will recommend checking state PDMP data for patients without a past-year check. (In Oregon, only prescribers are authorized to check PDMP data, so the NCM could not query the database him/herself.) PDMP checks are recorded in the medical record, so the research team will be able to track frequencies. If requested, the NCM may collaborate with pharmacy services to query state PDMP databases.
- c. The NCM will provide support about methods for talking with patients about prescription opioid adherence monitoring. This will include providing written information, such as scripts that clinicians can follow. In pilot interviews, PCPs requested these types of materials to assist with improving adherence to opioid regimens.
- d. The NCM will track all UDTs, notify the PCP of the results, and provide recommendations

about potential next steps in care. With collaboration from the primary care pain specialist and substance abuse specialist, the NCM will provide decision support to clinicians for patients with prescription opioid abuse about options for modifying treatment. The NCM will also follow-up to ensure treatment recommendations are implemented.

- e. With input from the NCM, some patients may be referred for supplemental treatment. This may include referral to the substance abuse treatment program, mental health clinic, or specialty pain service.
- f. The NCM may identify potential side effects or risky prescribing practices that have not been addressed.

Follow-up: Participants will complete assessments at baseline, 6 months, and 12 months post-baseline. During research visits, participants will complete all study measures, the structured clinical interview, and provide a UDT.

In the course of the study, a PCP or PACT nurse who is enrolled in the study may leave their position at the Portland VA. Clinical patients who are “attached” with these clinicians and already enrolled in the study will remain eligible to participate. Clinical recommendations that are made regarding patient’s care will continue to be forwarded to PACT team members who remain involved in each patient’s treatment.

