Aim 1: Evaluate to what extent a multifaceted intervention (ISOT) enhances prescription opioid safety. For Aim 1, we use 8.9 as an estimated standard deviation (SD) for change in COMM score from baseline to 12 months.⁹⁵ This SD estimate is based on SD's in prior intervention research.³³ For each group, an estimated SD for change was obtained using the two SD's and a within-subject intraclass correlation coefficient of 0.5. Averaging the corresponding variances leads to an estimated variance of 78 (SD=8.9). Power calculations were performed based on 28 or 32 (we may recruit as many as 40 PCPs, but do not anticipate that many will consent to participate) clinicians per intervention group and 4 or 5 patients per clinician. Table 1 displays differences in mean COMM change that can be detected under various values for the intraclass correlation coefficient. Our targeted sample size is 32 PCPs per group and an average of 5 patients per PCP. With a loss of 4 PCPs per group and 1 patient per PCP, we have power to detect small differences (able to detect $< \frac{1}{2}$ SD change) in COMM score. For Aim 1, we plan to conduct analyses for self-report data (COMM), clinical interviews to assess current substance use disorders (SCID), and results from research-administered UDTs. With n=320, 28-32 PCPs per group, and 4-5 patients per PCP, we have statistical power greater than 80% to detect differences in percentages between groups of about 20% for binary outcomes from the SCID and UDT (see Table 2 below for similar calculations for Aim 2).

Table 1. Mean differences in COMM change from baseline to 12 months (80% power, $\alpha=0.05$).

Intra-class correlation	Mean detectable difference in COMM change, n=4 patients per clinician, 28 clinicians per intervention	Mean detectable difference in COMM change, n=4 patients per clinician, 32 clinicians per intervention	Mean detectable difference in COMM change, n=5 patients per clinician, 28 clinicians per intervention	Mean detectable difference in COMM change, n=5 patients per clinician, 32 clinicians per intervention
0	3.4	3.2	3.0	2.8
0.02	3.5	3.3	3.2	2.9
0.04	3.6	3.4	3.3	3.1
0.10	3.9	3.6	3.6	3.4

Analyses for Aim 1: For comparison of mean COMM change between groups, we will use mixed longitudinal models with a random effect for PCP and patient, to allow for correlation between

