Clinicians will also be queried about perceived barriers and potential effectiveness of screening for prescription opioid abuse. With 32 pairs of clinicians and intra-class correlations of 0 to 0.1, we would have 80% power to detect differences of 0.50 to 0.53 SDs in mean summary scores between intervention groups.

Analyses for Aim 2: We will use GEE methods to compare between intervention groups the average numbers of clinical care documentations, UDT's, and queries to state prescription drug monitoring programs while adjusting for the baseline covariates (age, gender, depressive symptoms, history of SUD, and pain intensity) and the stratification variables. For patient level data, the approach for analysis of Aim 2 outcomes will be the same as that for Aim 1, using mixed models and/or GEE for comparisons, while adjusting for baseline covariates (age, sex, depressive symptoms, history of SUD, and pain severity), baseline measure of the outcome, and stratification variables (training type, proportion of panel prescribed opioids). Analyses will be conducted for scores on the Trust in Physician scale and Participatory Decision Making Style.

For clinician and PACT nurse data on barriers to use of UDTs, we will report descriptive information for each of the 10 questions. For each group and question, we will report the percentage of clinicians with scores at each of the five levels at baseline and follow-up, as well as the corresponding descriptive change information in follow-up scores. We will report the mean (and SD, min, max) of change for each question. We will obtain an overall survey score, by averaging the 10 question scores for each clinician and report the mean (and SD, min, max) survey score for each group at baseline and follow-up, along with the mean change (and SD, min, max) in survey score. We will use linear mixed models on the change scores to compare groups, while adjusting for clinician age, clinician training type, sex, panel size, summary survey score at baseline, and stratification variables. We will include a random pair effect to allow for correlation between the PCP and PACT nurse within each pair. P-values and 95% confidence intervals for the differences between groups in change scores will be provided. Similar analyses will be conducted for examining survey data on clinician satisfaction with ISOT.

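### The Aim 2 process-of-care power figure is for the percentage with any clinical urine drug test, but the planned analysis compares average numbers of tests

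*Combined protocol and SAP*

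**What the plan says.** All references are to the Combined protocol and SAP.

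- **Power (Data Analysis, Aim 2, and Table 2).** The calculation is introduced as "The power for comparing the percentage of patients receiving at least one UDT" and "assumes that 40% of patients in the control group will receive a follow-up UDT". The basis for the 40% is given as "This is based on prior research in which 26% of patients had a UDT", raised because control clinicians also attend the workshop. Table 2 lists detectable intervention percentages of 56% to 61%. The text concludes "We have 80% power to detect differences of 17-21% on binary outcomes" and expects the real differences to be much larger. PDMP checks are also discussed as percentages, with 3-5% of patients currently queried.
- **Analysis (Analyses for Aim 2).** The process outcomes are compared by GEE on "average numbers of clinical care documentations", UDTs and PDMP queries, adjusted for baseline covariates and the stratification variables. No comparison of any versus no clinical UDT, or any versus no PDMP check, is named.
- **Hypothesis and data.** Aim 2, Hypothesis 1 is worded in terms of frequency. Processes of Care Measures extracts the number of clinical UDTs and PDMP queries in the year before and the year during treatment, so both a count and an any/none indicator can be derived.
- **Intervention (System Assessment and Intervention, item a).** "For patients that have not been administered a UDT in 12 months or more, the NCM may assist the PCP by placing an order" describes one route by which testing would rise.

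**The concern.** A power statement belongs to one endpoint and one test. Here the endpoint in the power section (any UDT, yes or no) is not the endpoint in the analysis section (mean number of UDTs). The two can behave differently.

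The ordering prompt in item a acts on patients with no recent test. If its main effect is to move such patients from none to one, the percentage tested rises sharply but the mean rises by only a fraction of a test. Meanwhile a few often-tested patients dominate the variance of the count. In that case the planned test could miss the very change that Table 2 describes.

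Two passages might seem to supply the missing binary analysis, but neither does. The binary UDT model in Analyses for Aim 1 classifies opioid abuse from research-administered tests, and Processes of Care Measures keeps those apart from clinical tests. The sentence carrying the Aim 1 approach over to Aim 2 patient-level data could admit a binary model, but the outcomes then named are the Trust in Physician and Participatory Decision Making scores.

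**Working it through.** **1. Reproducing Table 2.** Inputs from the plan: 28 or 32 "clinicians per intervention group and 4 or 5 patients per clinician", ICC 0 to 0.10, control 40%, 80% power, alpha 0.05 (taken as two-sided).

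Effective n per arm = m × k / (1 + (m − 1) × ICC), for m patients in each of k clusters. Power for two proportions (pooled variance under the null) = Φ{[d√n − 1.96√(2p̄(1 − p̄))] / √(p1(1 − p1) + p2(1 − p2))}.

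Example, 4 × 28 at ICC 0.10: n = 112/1.3 = 86.2. At 61% versus 40%, (0.21 × 9.28 − 1.96 × 0.707)/√0.478 = 0.81, so power is 0.79. Solving for exactly 80% power gives 61.2% (stated 61%). All 16 cells agree after rounding (range 55.6% to 61.2%). The table spans 16 to 21 points, where the text says 17 to 21.

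**2. Binary test at 60% versus 40%, 32 × 5 per arm.** With n = 160: (0.2 × 12.65 − 1.386)/0.693 = 1.65, power 0.95. At ICC 0.02, n = 160/1.08 = 148.1 and power is about 0.94.

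**3. Count test, same percentages.** The documents give no mean, SD or dispersion, so the following are assumptions. Control counts are negative binomial with size k (smaller k means more dispersed) and 40% tested, so mean μ = k(0.6^(−1/k) − 1) and variance v = μ + μ²/k.

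*(a) Intervention only turns untested patients into exactly one test.* The mean rises by d = 0.2 and the intervention variance is v + μ² + d − (μ + d)². For k = 0.3: μ = 1.347 and v = 7.39; intervention variance = 7.39 + 1.81 + 0.20 − 2.39 = 7.01. SE = √((7.39 + 7.01)/160) = 0.300, 0.2/0.300 = 0.67, and power = Φ(0.67 − 1.96) = 0.10. This closed form ignores clustering. The table gives simulated power with a lognormal clinician effect (SD 0.2) and a t-test on clinician means, unadjusted and untransformed.

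| k | Tests per tested control patient (μ/0.4) | Power, 60% vs 40% | Power, 80% vs 40% |
|---|---|---|---|
| 0.3 | 3.4 | about 10% | about 26% |
| 0.5 | 2.2 | about 20% | about 62% |
| 1 | 1.7 | about 40% | about 92% |
| 3 | 1.4 | about 56% | about 99% |

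An unadjusted log-link Poisson GEE with robust errors gives similar figures (12/21/36/57% and 26/61/90/99%), so the result does not come from using a t-test.

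*(b) Intervention raises testing generally.* Same k in both arms, means set to give 40% and 60% tested. For k = 3 the means are 0.557 and 1.072, with log ratio 0.655. SE = √((1/0.557 + 1/1.072 + 2/3)/160) = 0.146, and power = Φ(0.655/0.146 − 1.96) = 0.99. Smaller k gives higher power. Repeated at the Table 2 percentages and designs, with common overdispersion from none (Poisson) to 4 (variance μ + 4μ²), power is 0.89 to above 0.99.

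*(c) In between.* At 58% versus 40% (32 × 4, ICC 0.02; binary power 0.80), with the same average of 1.0 to 2.0 tests per tested patient in both arms, count power is 0.62 to 0.78.

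**4. PDMP checks.** With 5% in control and the same one-check conversion, checks are so rare that count and indicator nearly coincide. Count power is already about 98-99% at 22% checked.

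**The case against.** The best case for leaving the plan alone has four parts.

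- **The low figures omit parts of the plan.** Analyses for Aim 2 adjusts patient-level outcomes for the baseline measure, prior-year counts are extracted, and Analyses for Aim 1 allows transformations. Under conversion-only at 80% versus 40%, log(1 + count) alone gives 94-100%. Baseline adjustment alone gives 64/85/96/99% across the four k values, if each patient's testing rate is stable from year to year. At 60% versus 40% the two together give 76-81%. Whether these provisions reach the count sentence is arguable, but they cannot be ignored.
- **Conversion-only is an extreme effect model.** The nurse care manager also tracks all tests, monitors records and follows up on recommendations, and the plan expects much higher testing rates.
- **The worst row has no support in the documents.** It implies 3.4 clinical tests a year per tested control patient, while the Background describes regular testing as uncommon.
- **Counts match the hypothesis**, which is about more frequent tests and queries.

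All four stand. They rule out the inference a reader might draw that the count test is underpowered, or that counts should give way to percentages as the main analysis. They do not supply the missing any/none analysis, and they do not make Table 2 apply to a comparison of means.

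**Conclusion.** The mismatch is real and minor. For UDTs and PDMP queries, the stated 80% power attaches to a comparison that is not in the analysis plan, and nothing in the documents allows it to be carried over to the count test. At 32 × 5 per arm and 60% versus 40% tested, count power runs from about 10-56% (conversion-only, raw counts) to about 99% or more (general rise). Both ends rest on assumed count distributions. For PDMP checks the practical effect is negligible if control stays near the current 3-5%.

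A reader might infer that Aim 2 as a whole is powered for the wrong endpoint. It is not: power for the trust, decision-making and clinician-survey scores is stated for means and matches analyses of means. The sample-size target is presented with the primary outcome, COMM, and is untouched. If the effect on any UDT is as large as the plan expects, the added binary comparison would be well powered: at 70% versus 40%, about 0.98 even with 28 × 4 and ICC 0.10.

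**What to change.** In Analyses for Aim 2, add a pre-specified comparison of the percentage of patients with at least one clinical UDT, and with at least one PDMP check, in the 12 months of follow-up. Use the binary GLMM or GEE from Analyses for Aim 1, with the same covariates, the prior-year value and the stratification variables. State that Table 2 refers to this comparison.

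Keep the mean-count GEE for the frequency hypothesis, and specify a log link with robust or overdispersed variance. Say in advance which question each analysis answers, so that a disagreement between them is not settled after the data are seen.

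The cost is a few lines of SAP text and one extra model per outcome. The data are already being extracted, and no change to sample size or conduct is needed.
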